6.3.2 Treatment of Ipilimumab-Related Isolated Drug Fever

In the event of isolated drug fever, the investigator must use clinical judgment to determine if the fever is related to the ipilimumab or to an infectious etiology. If a patient experiences isolated drug fever, for the next dose, pre-treatment with acetaminophen or non-steroidal anti-inflammatory agent (investigator discretion) should be instituted and a repeated antipyretic dose at 6 and 12 hours after ipilimumab infusion, should be administered. The infusion rate will remain unchanged for future doses. If a patient experiences recurrent isolated drug fever following premedication and post dosing with an appropriate antipyretic, the infusion rate for subsequent dosing should be decreased to 50% of the previous rate. If fever recurs following infusion rate change, the investigator should assess the patient's level of discomfort with the event and use clinical judgment to determine if the patient should receive further ipilimumab.

6.4 Monitoring and Management of Immune-mediated Adverse Reactions

6.4.1 Immune-mediated Enterocolitis

The clinical presentation of GI immune-related AEs included diarrhea, increase in the frequency of bowel movements, abdominal pain, or hematochezia, with or without fever. However inflammation may occur in any part of the GI tract including esophagitis and gastritis. Fatalities due to GI perforation have been reported in clinical trials of ipilimumab. Patients should be carefully monitored for GI symptoms that may be indicative of immune-related colitis, diarrhea, or GI perforation. Diarrhea or colitis occurring after initiation of ipilimumab therapy should be evaluated to exclude infectious or alternate etiologies. In clinical trials, immune-related colitis was associated with evidence of mucosal inflammation, with or without ulcerations, and lymphocytic infiltration.

Monitor patients for signs and symptoms of enterocolitis (such as diarrhea, abdominal pain, mucus or blood in stool, with or without fever) and bowel perforation (such as peritoneal signs and ileus). In symptomatic patients, rule out infectious etiologies and consider endoscopic evaluation to establish etiology and for persistent or severe symptoms. *C. difficile* toxin has been detected in several patients with colitis and may be an independent entity or may co-exist with ipilimumab induced inflammatory colitis.

Withhold ipilimumab dosing for any patients with enterocolitis pending evaluation; administer anti-diarrheal treatment and, if persistent evaluate with colonoscopy and initiate systemic corticosteroids at a dose of 0.5 mg/kg/day prednisone or equivalent.

Permanently discontinue ipilimumab in patients with severe enterocolitis and initiate systemic corticosteroids at a dose of 1 to 2 mg/kg/day of prednisone or equivalent. Upon improvement to grade 1 or less, initiate corticosteroid taper and continue to taper over at least one month. In clinical trials, rapid corticosteroid tapering has resulted in recurrence or worsening symptoms of enterocolitis in some patients.

Patients have been treated with anti-TNF agents for persistent colitis not responding to steroids.

Please note autoimmune pancreatitis may cause abdominal pain and should be included in all evaluations. Enteritis may occur occasionally with other autoimmune events including hepatitis, pancreatitis, and endocrine insufficiency, which should be evaluated as clinically indicated.

6.4.2 Immune-mediated Hepatitis and Pancreatitis

Hepatic immune-related AEs were mostly clinically silent and manifested as transaminase or bilirubin laboratory abnormalities. Fatal hepatic failure has been reported in clinical trials of ipilimumab. **Serum transaminase and bilirubin and lipase levels must be evaluated before each dose of ipilimumab as early laboratory changes may be indicative of emerging immune-related hepatitis/ pancreatitis and elevations in liver function tests (LFTs) may develop in the absence of clinical symptoms.** Increase in LFT or total bilirubin should be evaluated to exclude other causes of hepatic injury, including infections, disease progression, or other medications, and monitored until resolution. Liver biopsies from patients who had immune-related hepatotoxicity showed evidence of acute inflammation (neutrophils, lymphocytes, and macrophages).

Monitor liver function tests (hepatic transaminase and bilirubin levels, lipase) and assess patients for signs and symptoms of hepatotoxicity/ pancreatitis before each dose of ipilimumab. In patients with hepatotoxicity, rule out infectious or malignant causes and increase frequency of liver function test monitoring until resolution. Withhold ipilimumab in patients with grade 2 hepatotoxicity.

Permanently discontinue ipilimumab in patients with grade 3–5 hepatotoxicity/pancreatitis and administer systemic corticosteroids at a dose of 1 to 2 mg/kg/day of prednisone or equivalent. When liver function tests show sustained improvement or return to baseline, initiate corticosteroid tapering and continue to taper over 1 month. Across the clinical development program for ipilimumab, mycophenolate treatment has been administered in patients who have persistent severe hepatitis despite high-dose corticosteroids.

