 - In the absence of disease, patients must have an absolute neutrophil count $\geq 500 \times 10^9 / L$ or platelet count to $\geq 25,000 \times 10^9 / L$ to proceed.
 - Hematologic criteria to start cycle 4:
 - If there is persistent disease (e.g. peripheral blasts, any marrow disease, persistent leukemia cutis or other form of extramedullary

disease), then there are no hematologic requirements to start cycle .

- In the absence of disease, patients must have an absolute neutrophil count $\geq 500 \times 10^9/L$ or platelet count to $\geq 25,000 \times 10^9/L$ to proceed; otherwise administration of treatment will be delayed.

- **Treatment**

- Decitabine 20 mg/m² IV daily over 60 minutes (+/- 15 minutes) x 5 consecutive doses on **days 1-5** every 4 weeks given per institutional guidelines
 - **Pre-medication prior to chemotherapy:** per institutional standards
- Ipilimumab IV (per dose level as in table above) on **day 1** over 90 minutes (+/- 15 minutes) every 4 weeks for a total of 4 doses during induction
 - Dose escalation levels: 3 mg/kg (**starting dose**, dose level 0), 5 mg/kg (dose level 1), and 10 mg/kg (dose level 2)
 - Dose de-escalation level: 1 mg/kg
- Decitabine will be dosed prior to ipilimumab on day 1
- Vitals signs will be repeated hourly from time of ipilimumab infusion for up to two hours after infusion ends (+/- 30 minutes) on day 1 after first dose and up to one hour after infusion ends (+/- 30 minutes) on day 1 for subsequent doses.

- Clinic visits (including physical exam, medication review, ECOG and AE review)
 - Cycle 1: on day 1 and day 15 (+/- 3 days)
 - Cycles 2-4: on day 1 (+/- 3 days).

- **Procedures:**

- Labs
 - Cycle 1: on day 1, day 15 (+/- 3 days).
 - Cycles 2-4: on day 1 (+/- 3 days).
 - End of cycles 1, 2 and 4 on day of bone marrow biopsy (on a day between days 24-28).
- Bone marrow biopsy (including aspirate (if aspirable), core, flow cytometry, cytogenetics) will be at the end of cycles 1, 2 and 4 (on a day between days 24-28) for response assessment.
- If sole extramedullary disease (unless leukemia cutis), routine evaluation may include PET imaging (if FDG avid at time of diagnosis) at the end of cycles 2 and 4 (on a day between days 24-28) for response assessment.

- **Correlative studies:** peripheral blood and aspirate collection at the end of cycles 1, 2 and 4 on a day between days 24-28 (see correlative calendar in [section 10.2](#)).

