- The DLT window will be the first 8 weeks of combination treatment with decitabine and ipilimumab (starting day 1 of cycle 1).
- At the time of response assessments, patients with evidence of disease progression will come off study unless they have evidence of treatment tolerability and clinical benefit (i.e. improvement in transfusion frequency or peripheral blast reduction or symptom improvement). Patients with evidence of disease progression may be allowed to stay on study if deriving clinical benefit with approval from the overall PI as there may be a delayed response with

- immunotherapy.
- Patients with stable disease or better at the end of cycle 4 will move forward with treatment in the maintenance phase.
- **Cycles 5-12: Maintenance phase with combination decitabine and ipilimumab**
 - Pre-treatment Criteria
 - In the absence of disease, patients should have an absolute neutrophil count $\geq 500 \times 10^9/L$ or platelet count to $\geq 25,000 \times 10^9/L$ to proceed with each cycle. Dose delay recommendations are provided in section 6.
 - If there is still disease (partial or stable) then no hematologic requirements are required to start cycle
 - Treatment
 - Decitabine 20 mg/m² IV daily over 60 minutes (+/- 15 minutes) x 5 consecutive doses on **days 1-5** every 4 weeks given per institutional guidelines
 - **Pre-medication prior to chemotherapy:** per institutional standards
 - Ipilimumab IV (per dose level as in table above) on **day 1** over 90 minutes (+/- 15 minutes) every **8 weeks** for a total of 4 doses during maintenance
 - Decitabine will be dosed prior to ipilimumab on day 1
 - Vitals signs will be repeated hourly from time of ipilimumab infusion for up to one hour after infusion ends (+/- 30 minutes) on day 1.
 - Clinic visits (including physical exam, medication review, ECOG and AE review)
 - Cycles 5-12: on day 1 (+/- 3 days).
 - Procedures:
 - Labs
 - Cycles 5-12: on day 1 (+/- 3 days).
 - At the end of cycles 7 and 10 on a day between days 24-28 and at end of study on a day between days 24-28.
 - Bone marrow biopsy (including aspirate (if aspirable), core, flow cytometry, cytogenetics) will be at the end of cycles 7, 10 and at end of study (on a day between days 24-28) for response assessment.
 - Correlative studies: peripheral blood and aspirate collection at the end of cycles 7 and 10 on a day between days 24-28 and at the end of study (see correlative calendar in [section 10.2](#)).

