Doses of ipilimumab will be referred to as dose #1, dose #2, dose #3, or dose #4 during the induction phase and dose #5, dose #6, dose #7 or dose #8 during the maintenance phase. The induction phase will include the first four doses of ipilimumab and the maintenance phase will include the last four doses of ipilimumab. If there are any ipilimumab dose delays, the cycle and day will not change. The “study cycle” number is determined by the cycle of decitabine that the patient is on (with “cycle 1” starting as the first cycle of COMBINATION with ipilimumab; the priming phase of decitabine monotherapy could be considered “cycle 0” for purposes of this study). If there is a delay in ipilimumab dosing, decitabine may be continued as scheduled. Disease response assessments will be as scheduled regardless of how many doses of ipilimumab is administered. As an example, if dose #2 of ipilimumab (which would be due on cycle 2 day 1) is delayed for four weeks due to an ipilimumab related toxicity, decitabine can still be administered on cycle 2 days 1-5 and the scheduled disease response assessment will still occur at the end of cycle 2. If the ipilimumab related toxicity has resolved by cycle 3 day 1, then dose #2 of ipilimumab will be given then concurrent with decitabine. Continuing decitabine will help to maintain disease control given the proliferative nature of AML. We will capture how many doses of ipilimumab that patients are able to receive in this study.

Delay window: If ipilimumab dosing must be delayed for > 4 weeks +/- 3 days for holiday or scheduling logistics (more than 8 weeks [+/- 3 days] since the prior dose administration), then patients must come off treatment. For example, if patient cannot receive ipilimumab on cycle 2 day 1 due to development of grade 2 colitis, then the patient’s dose will be delayed to cycle 3 day 1. If the patient cannot be dosed on cycle 3 day 1 (and it has now been more than 8 weeks since last dose), then the patient must come off treatment.

Exceptions may be made to hold ipilimumab for > 8 weeks after discussion with overall PI for grade 2 or lower ipi-induced immune related AEs and GVHD events that are less than grade III.

Patients may remain on decitabine alone until ipilimumab can be re-introduced if patients demonstrate continued benefit and resolution of suspected ipilimumab-induced AE to grade 1 or baseline (skin GVHD can be controlled with topical steroids).

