c: Albumin, alkaline phosphatase, total bilirubin, bicarbonate, BUN, calcium, chloride, creatinine, glucose, potassium, total protein, SGOT [AST], SGPT [ALT], sodium, uric acid, magnesium, phosphorus.

d: Every 3 months unless clinically indicated: gamma-GT, direct bilirubin, LDH, TSH, and lipase

e: Please see [Appendix F](#) for helpful study check list including immune related AE evaluation

f: PET scans are required only for those with sole extramedullary disease (no marrow involvement by morphology) and optional for those with extramedullary and marrow involved AML. PET scans are standard imaging tests for those with extramedullary disease involvement. Study can be performed any time between day 24-28 at the end of cycles 2 and 4 (suggested time frame). However as clinical scenario may vary with patients with sole extramedullary disease, we will allow imaging window of +/- 4 weeks based on clinical scenario or scheduling logistics. Please send report and imaging (on CD) with redacted PHI for central review of extramedullary AML events to Attn: [name], Research Project Manager for CTEP 10026; Dana-Farber Cancer Institute; [name]. If there are reports only, please fax to [contact] or email to: [contact]

g: If patient has sole extramedullary disease and there was no resolution of FDG-avid disease by the end of cycle 2, then patients should have a repeat PET at the end of cycle 4 per standard of care. Study can be performed any time between day 24-28 at the end of cycles 2 and 4 (suggested time frame). However as clinical scenario may vary with patients with sole extramedullary disease, we will allow imaging window of +/- 4 weeks based on clinical scenario or scheduling logistics. Please send report and imaging (on CD) with redacted PHI for central review of extramedullary AML events to Attn: [name], Research Project Manager for

CTEP 10026; Dana-Farber Cancer Institute; [name]. If there are reports only, please fax to [contact] or email to: [contact]

- h: Serum pregnancy test (women of childbearing potential).- Negative results required within 72 hours of treatment start

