- n: For those with known HIV they must get a CD4 count and an HIV viral load (PCR).
- o: Baseline echocardiogram and EKG required for screening (if done within 4 weeks of treatment start does not need to repeat unless there is a clinical concern) and at any other time that is clinically indicated during the trial as it relates to footnote q
- p: Peripheral blood, aspirate, core biopsy, or FFPE to be collected per schedule described correlative table below.
- q: Alert PI if there is concern for cardiac toxicity (minimum assessment: cardiology consult, EKG, echocardiogram, and labs CPK and troponin; refer to section 6.4.7)
- r: Please see section 7.3.5 of the protocol for reporting requirements for GVHD and suspected immune related AEs to enable central review
- s: MUGA scan is a suitable alternative to an echocardiogram
- t: For participants enrolled on Arm A (post transplant), a formal GVHD assessment is required at minimum on Day 1 of each cycle utilizing the GVHD assessment worksheet provided in Appendix B

	Maintenance cycles and end of study										
	C5 D1 ^b	C6 D1 ^b	C7 D1 ^b	C7 D24 ^a	C8 D1 ^b	C9 D1 ^b	C10 D1 ^b	C10 D24 ^a	C11 D1 ^b	C12 D1 ^b	End of study ^{i,j}
Ipilimumab^A	X		X			X			X		
Decitabine^B	X	X	X		X	X	X		X	X	
Concurrent meds	X	X	X		X	X	X		X	X	
Physical Exam	X	X	X		X	X	X		X	X	X ^k
Vital signs	X	X	X		X	X	X		X	X	
Height	X										
Weight	X	X	X		X	X	X		X	X	
Performance status	X	X	X		X	X	X		X	X	
CBC w/diff, plts	X	X	X	X	X	X	X	X	X	X	X
Serum chemistry^c	X	X	X		X	X	X		X	X	X
Immune-related labs^d			X				X				X
Adverse event evaluation^{e,f,m}	X	X	X		X	X	X		X	X	X ^k
GVHD Assessment	X	X	X		X	X	X		X	X	X
Bone marrow^f				X ^f				X			X ^f
T cell chimerism^g											X
Correlative studies^h				X				X			X

A: Ipilimumab: Dose as assigned by dose level. Administered every 8 weeks. Dosed per weight on day 1 of a cycle.
B: Decitabine: 20 mg/m² daily IV for 5 consecutive days on days 1-5. Dosed per weight on day 1 of the lead in
a: Can be done any time between day 24-28
b: +/- 3 days
c: Albumin, alkaline phosphatase, total bilirubin, bicarbonate, BUN, calcium, chloride, creatinine, glucose, potassium, total protein, SGOT [AST], SGPT [ALT], sodium, uric acid, magnesium, phosphorus.
d: At baseline, C1D1, and then every 3 cycles thereafter or more frequently when clinically indicated: gamma-GT, direct bilirubin, LDH, TSH, and lipase
e: Please see [Appendix F](#) for helpful study check list including immune related AE evaluation

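### Lipase is required before each ipilimumab dose in section 6.4.2, but the calendar leaves 4 to 6 of 8 doses without a scheduled value and has no post-dose draw in the DLT window

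*Combined protocol and SAP*

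**What the plan says.** Section 6.4.2 sets the requirement: "Serum transaminase and bilirubin and lipase levels must be evaluated before each dose of ipilimumab". Its next paragraph repeats it: "Monitor liver function tests (hepatic transaminase and bilirubin levels, lipase) and assess patients for signs and symptoms of hepatotoxicity/ pancreatitis before each dose of ipilimumab".

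The dosing plan has eight ipilimumab doses. Section 6.2 states: "The induction phase will include the first four doses of ipilimumab and the maintenance phase will include the last four doses of ipilimumab". Section 5.1 gives ipilimumab "every 4 weeks for a total of 4 doses during induction", then every 8 weeks "for a total of 4 doses during maintenance". The calendar places these on day 1 of cycles 1, 2, 3, 4, 5, 7, 9 and 11.

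The section 10.1 calendar lists lipase only under immune-related labs:

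- **Induction table:** marked at pre-study, C1D1 and C4D24 (window days 24-28). Footnote d reads "Every 3 months unless clinically indicated: gamma-GT, direct bilirubin, LDH, TSH, and lipase".
- **Maintenance table:** marked at C7D1, C10D1 and end of study. Its footnote d gives baseline, C1D1, then "every 3 cycles thereafter or more frequently when clinically indicated".
- **Serum chemistry (footnote c in both tables):** drawn on every ipilimumab day 1. It contains AST, ALT and total bilirubin, but not lipase.

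Appendix F, the pre-treatment checklist, puts lipase among labs done every 3 months. Its review before ipilimumab covers AST, ALT and total bilirubin only. Section 5.1 schedules labs on day 1 of each cycle without listing their contents.

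**The concern.** A mandatory pre-dose test is missing from the two tools that sites use at the visit, the calendar and the checklist. Two things depend on it.

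**Dosing decisions.** Section 6.2 requires a delay for a related non-hematologic laboratory abnormality of grade 3 or higher. Section 6.4.2 requires permanent discontinuation for pancreatitis of grade 3 to 5, and gives as its reason for testing that early laboratory changes may be the first sign. Without a pre-dose value, these rules cannot be applied to a silent rise.

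**DLT ascertainment.** Section 5.2 counts treatment-related non-hematologic toxicity of grade 3 or higher in the first 56 days of combination therapy, and lipase is not a named exception. With three to six patients per dose level, one DLT can change the escalation decision. Section 6.4.6 says immune-related events commonly begin 3 to 10 weeks after the first dose, that is, about days 21 to 70. The calendar has no lipase draw in that period.

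**Working it through.** The plan states no figure for lipase coverage, so the check is a count from the calendar. The planned total of 8 doses is reproduced: 4 in induction plus 4 in maintenance.

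**Study day** = (cycle - 1) x 28 + day within cycle, counted from C1D1.

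- Ipilimumab at C1, C2, C3, C4, C5, C7, C9 and C11, day 1: days 1, 29, 57, 85, 113, 169, 225 and 281.
- Lipase by the tables: C1D1 = day 1; C4D24-28 = 3 x 28 + 24 to 3 x 28 + 28 = days 108-112; C7D1 = day 169; C10D1 = 9 x 28 + 1 = day 253; plus pre-study and end of study.
- Lipase by the maintenance footnote read literally (C1D1, then every 3 cycles): C1D1, C4D1, C7D1 and C10D1 = days 1, 85, 169 and 253.

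**Crediting rule.** Section 6.4.2 sets no look-back limit, so several rules were tried. In each, a draw counts for a dose only if it falls after the previous dose; otherwise one value would serve two doses.

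| Source of draws | Draws credited | Doses covered | Doses without lipase |
|---|---|---|---|
| Tables | Same day only | C1, C7 | C2, C3, C4, C5, C9, C11 (6 of 8) |
| Tables | Up to 7 days before | C1, C5, C7 | C2, C3, C4, C9, C11 (5 of 8) |
| Tables | Up to 28 days before | C1, C5, C7, C11 | C2, C3, C4, C9 (4 of 8) |
| Footnote, literal | Same day only | C1, C4, C7 | C2, C3, C5, C9, C11 (5 of 8) |
| Footnote, literal | Up to 28 days before | C1, C4, C7, C11 | C2, C3, C5, C9 (4 of 8) |

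Two draws drive the range. C4D24 is 113 - 108 = 5 days before the C5 dose. C10D1 is 281 - 253 = 28 days before the C11 dose. Doses at C2, C3 and C9 are uncovered under every rule.

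**DLT window, days 1-56.** The only scheduled lipase is at C1D1, taken here as drawn before the first dose. The next is day 108-112 by the tables or day 85 by the footnote. Scheduled post-dose draws in the window: 0 either way.

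**Comparison.** AST, ALT and total bilirubin are scheduled on all 8 dose days, so the gap concerns lipase and not the other tests named in section 6.4.2.

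**If section 6.4.2 were carried into the calendar,** all 8 doses would have a value. The C2D1 draw (day 29) would fall inside the DLT window; C3D1 (day 57) is nominally one day outside.

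**The case against.** The strongest reply is that nothing is lost, because section 6.4.2 still binds sites. A site that obeys it draws lipase before C2D1, on about day 29. Both footnotes also leave room for clinically indicated tests, and a patient who leaves early has an end-of-study draw. This stands against one tempting inference, that a silent rise cannot be seen in the DLT window. The documents support only that no draw is scheduled there for a patient who continues treatment. It does not remove the conflict: indicated draws depend on suspicion, and section 6.4.2 wants the test in the absence of symptoms.

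A second reply is that sections 6.2.2 and 6.3 describe this material as suggested guidance. That leaves open which text governs, but the lipase sentence itself says must. For TSH, section 6.4.5 explains why clinical monitoring may be as sensitive as testing before each infusion; no such latitude is given for lipase.

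Third, a reader might infer that every grade 3 lipase rise is a DLT, so the count is too low. Section 5.2 does not support that. The event must be at least possibly related to the combination and not to disease, intercurrent illness or decitabine alone, and grade 3 immune-related events that respond to corticosteroids and improve to grade 1 or less within 4 weeks are exempt. Section 7.1.1 also lists raised lipase among events with insufficient evidence of causation, though pancreatitis is on its possibly related list. Section 6.4.6 puts pancreatitis below 1%. Undercounting is possible but not shown.

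Fourth, the C4D24 mark may be misplaced. The performance status row is also marked there and not at C3D1 or C4D1, although section 5.1 puts ECOG on day 1 of cycles 2-4. This is why day 85 is given beside day 108-112; both lie beyond day 56. The difference between 3 months and 3 cycles (84 days) is minor in itself.

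**Conclusion.** The inconsistency is real under every reading tried. Section 6.4.2 requires lipase before each ipilimumab dose, and the calendar and Appendix F do not schedule it that way. The shortfall is 4 to 6 of 8 planned doses. It is 5 of 8 if C4D24-28 is credited to C5 and C10D1 is not credited to C11, but a reader should not take 5 as exact, because section 6.4.2 states no look-back. No post-dose lipase is scheduled in the 56-day DLT window.

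The consequence is a possible missed silent, treatment-related rise of grade 3 or higher, at dosing decisions and in the DLT count, within the attribution and steroid-response limits of section 5.2. Its size cannot be computed, since the documents give no rate of asymptomatic lipase elevation for this combination. The result assumes nominal visit days, the calendar marks as read, and patients who remain on treatment through the window.

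**What to change.** Reconcile section 6.4.2, both section 10.1 tables with their footnotes d, and Appendix F so that all state one lipase schedule. Which schedule governs is the sponsor's decision.

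If the sponsor confirms section 6.4.2, list lipase with the labs already drawn on day 1 of cycles 1-4, 5, 7, 9 and 11, and add it to the Appendix F review before ipilimumab. The C2D1 draw would then give a post-dose value inside the DLT window. A separate draw at the end of cycle 2 is not needed for this reconciliation, and no section asks for one.

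If the sponsor confirms the calendar instead, amend both statements in section 6.4.2 and make the two footnotes and the C4 mark agree.

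The cost is an edit to the protocol text and calendar and, in the first case, one extra analyte on existing blood draws.
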